 - Known severe or oxygen dependent bronchoconstrictive or bronchospastic lung disease [e.g., asthma, wheezing, chronic obstructive pulmonary disease (COPD), etc.].
 - Sick sinus syndrome
 - History of heart transplantation.
 - Dialysis
 - Subject requires emergent cardiac medical intervention or catheterization after the clinical study.
 - Documented myocardial infarction (MI) ≤ 30 days prior to enrollment.
 - History of percutaneous coronary intervention (PCI) ≤ 4 weeks prior to enrollment.

- History of coronary artery bypass graft (CABG) \leq 8 weeks prior to enrollment.
- Severe LV dysfunction, with ejection fraction of $< 30\%$
- Serious non-cardiac medical illness (e.g., disseminated malignancy, severe neurological dysfunction at time of baseline PET study) or a social situation which will preclude research study participation
- History of seizure disorder

Discontinuation criteria:

Subjects should be discontinued for the following discontinuation criteria

- Subject does not fulfill inclusion or exclusion criteria
- Subject experiences a serious or intolerable adverse event
- In the Investigator's opinion, the subject is non-compliant with the protocol requirements (protocol violation)
- Subject's health would be jeopardized by continued participation
- Subject wishes to withdraw consent

Lexiscan will not be administered to patients with clinical or EKG evidence on ischemia during exercise treadmill testing. Clinical or EKG abnormalities during treadmill testing that would preclude administration of Lexiscan are listed below:

- a) Clinical
 - a. Severe chest pain
 - b. Severe lightheadedness or dizziness,
 - c. Severe shortness of breath
 - d. Exercise induced hypotension ($> 10\text{mm Hg}$ decrease in systolic blood pressure)
 - e. Exercise induced hypertension (systolic blood pressure $> 210\text{ mm Hg}$)
- b) ECG changes
 - a. Significant ST segment depression ($\geq 2\text{ mm}$)
 - b. Significant ST segment elevation ($\geq 1\text{ mm}$)
 - c. Sustained ventricular or atrial tachycardia,
 - d. Exercise induced heart block

Statistical Plan:

The overall aim of this pilot study of 50 patients is to assess the tolerability, safety, diagnostic accuracy and image quality between Lexiscan with symptom limited exercise compared to Lexiscan alone.

Aim 1. For this aim, we will compare the reported side effect profile for Lexercise to Lexiscan PET, using a Pearson Chi square test. A P-value of <0.05 will be considered significant.

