
- Contraindications to exercise stress testing such as
 - unstable angina
 - known severe left main coronary artery stenosis
 - severe or uncontrolled heart failure
 - uncontrolled atrial or ventricular arrhythmias
 - symptomatic hypotension or severe hypertension (systolic blood pressure < 90 or > 200 mmHg, respectively)
 - > 1st degree atrioventricular block in the absence of a functioning pacemaker.
- Contraindications to Lexiscan use such
 - Allergy or intolerance to aminophylline or regadenoson
 - Known severe or oxygen dependent bronchoconstrictive or bronchospastic lung disease [e.g., asthma, wheezing, chronic obstructive pulmonary disease (COPD), etc.].
 - Sick sinus syndrome
- History of heart transplantation.
- Dialysis
- Subject requires emergent cardiac medical intervention or catheterization after the clinical study.
- Documented myocardial infarction (MI) ≤ 30 days prior to enrollment.
- History of percutaneous coronary intervention (PCI) ≤ 4 weeks prior to enrollment.
- History of coronary artery bypass graft (CABG) ≤ 8 weeks prior to enrollment.
- Severe LV dysfunction, with ejection fraction of < 30%
- Serious non-cardiac medical illness (e.g., disseminated malignancy, severe neurological dysfunction at time of baseline PET study) or a social situation which will preclude research study participation
- History of seizure disorder

Discontinuation criteria:

Subjects should be discontinued for the following discontinuation criteria

- Subject does not fulfill inclusion or exclusion criteria

- Subject experiences a serious or intolerable adverse event
- In the Investigator's opinion, the subject is non-compliant with the protocol requirements (protocol violation)
- Subject's health would be jeopardized by continued participation
- Subject wishes to withdraw consent

Lexiscan will not be administered to patients with clinical or EKG evidence on ischemia during exercise treadmill testing. Clinical or EKG abnormalities during treadmill testing that would preclude administration of Lexiscan are listed below:

c) Clinical

- a. Severe chest pain
- b. severe lightheadedness or dizziness,
- c. severe shortness of breath
- d. exercise induced hypotension (> 10mm Hg decrease in systolic blood pressure)
- e. exercise induced hypertension (systolic blood pressure >210 mm Hg)

d) ECG changes

- a. Significant ST segment depression (≥ 2 mm)
- b. Significant ST segment elevation (≥ 1 mm)
- c. Sustained ventricular or atrial tachycardia,

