- Sub diaphragmatic activity (liver heart ratios)
- Defect contrast
- Signal to noise ratio and
- Dynamic image evaluability will be assessed

VI. BIOSTATISTICAL ANALYSIS

The overall aim of this pilot study of 50 patients is to assess the tolerability, safety, diagnostic accuracy and image quality between Lexiscan with symptom limited exercise compared to Lexiscan alone.

Aim 1. For this aim, we will compare the reported side effect profile for Lexercise to Lexiscan PET, using a Pearson Chi square test. A P-value of <0.05 will be considered significant.

Aim 2: For this aim, we will compare objective measures of image quality including signal to noise ratio using dynamic Rubidium-82 images or N-13 ammonia, the frequency of misregistration between PET and CT, the frequency of presumed motion artifact and bowel radiotracer activity. These measures will be compared using a student's t-test or a Pearson Chi square test, as appropriate. A P-value of <0.05 will be considered significant.

Aim 3: For this aim, we seek to compare measures of semi quantitative relative perfusion, absolute perfusion and LVEF using the Lexiscan alone compared to Lexercise PET. Firstly, we will compare semi-quantitative defect size, severity and reversibility between the Lexercise and Lexiscan PET studies. Based on the results of one prior study using N-13 ammonia and comparing dipyridamole versus treadmill exercise², a sample size of 35 subjects with reversible defects should be adequate to identify if significant differences exist between Lexercise and Lexiscan PET protocols. Next, we will study the changes in LVEF from rest to peak stress in Lexercise versus Lexiscan PET studies in the normal and ischemic subjects. Finally, we will compare regional rest and peak stress myocardial blood flow and coronary flow reserve between Lexercise and Lexiscan PET studies.

VII. RISKS AND DISCOMFORT

Time: Participation in this trial entails an exercise vasodilator stress Rubidium-82 PET or N-13 ammonia scan. The total time spent for the study procedures is approximately 1 hour.

Intravenous line insertion: Possible side effects intravenous line insertion are pain, bruising, or infection where the needle entered the skin. Some people faint or get dizzy during insertion of the intravenous line.

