No direct benefit is anticipated to individual subjects. The results of this study may benefit society through evaluation of the diagnostic utility of novel protocol utilizing combined symptom limited exercise vasodilator stress test to image endothelium dependent and endothelium independent factors affecting myocardial blood flow.

IX. MONITORING AND QUALITY ASSURANCE

Subject safety will be ensured by strict adherence to inclusion and exclusion criteria and close monitoring. Subjects that experienced serious adverse events during the study will be removed from the study and followed up, but no other study procedures will be performed. We will monitor the subjects closely for seizures and ischemic symptoms. History of seizures is an exclusion criteria for the study. Individuals who experience seizures for the first time during the initial regadenoson study will be excluded from the second regadenoson with exercise study. Intravenous aminophylline, a competitive agonist, will be administered for ischemic symptoms. Subjects with ischemic symptoms will be monitored until complete resolution (current clinical practice). As listed in page 22, study endpoints, safety blood work will be drawn after the Lexiscan and the Lexercise PET study to measure serum troponin T levels. This study does not involve treatment and hence a data safety monitoring board.

This is a pilot clinical study of about 50 subjects. The study PI, [name], will be responsible for monitoring the study procedures after every subject is enrolled, including the accuracy and completeness of the case report form entries, source documents and informed consent after every enrollment. These documents will be appropriately maintained on submission.

Specification of Source Documents

The following information will be included in the source medical records:

- Demographic data (age, sex, and race)
- Inclusion and exclusion criteria details
- Participation in study and signed and dated informed consent forms
- Visit dates
- Medical history and physical examination details
- Key efficacy and safety data
- Adverse events and concomitant medication
- Results of relevant examinations
- Laboratory printouts
- Reason for premature discontinuation

Ethical Conduct of the Study

The investigator(s) and all parties involved in this study will conduct the study in adherence to GCP, ICH Guidelines and the applicable laws and regulations.

Subject Confidentiality

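### Withholding Lexiscan for treadmill ischemia or severe symptoms removes Lexercise pairs selectively, and no analysis set, denominator or sample-size allowance covers those subjects

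*Combined protocol and SAP*

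**What the plan says.** The Synopsis (Discontinuation criteria) states that "Lexiscan will not be administered to patients with clinical or EKG evidence on ischemia during exercise treadmill testing", and the Subject Selection section repeats the rule. The list that follows names severe symptoms (for example "Severe chest pain"), a fall in systolic pressure of more than 10 mm Hg or a value above 210 mm Hg, ST depression of at least 2 mm or elevation of at least 1 mm, sustained tachycardia, and heart block. The abbreviation list defines Lexercise as Lexiscan plus exercise. The image acquisition text in Study Procedures runs from treadmill to regadenoson to tracer, with no branch for a subject whose regadenoson is withheld.

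For Aim 1, the Synopsis and section VI say "we will compare the reported side effect profile for Lexercise to Lexiscan PET", using a Pearson chi-square test. No denominator is named. For Aim 3, defect size, severity and reversibility are compared between the two protocols; no analysis set, missing-data rule, replacement rule or allowance for loss is given. The Synopsis calls 24 subjects with reversible defects adequate; section VI says 35.

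Section IX adds: "Subjects that experienced serious adverse events during the study will be removed from the study and followed up". The same sentence goes on to rule out further study procedures.

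**The concern.** The triggers for withholding are themselves tolerability and ischemia outcomes. Hypothesis 3 rests on exercise reducing flow in diseased territories, and the Background offers true ischemia as a possible reason why exercise defects are larger. The subjects most likely to lose their Lexercise scan are thus probably among those in whom the hypothesised effect is strongest. The study also recruits patients because they have reversible defects, so such losses are foreseeable.

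At stake in Aim 3 are the number of pairs and the size of the observed difference; a null result would be hard to interpret. At stake in Aim 1 is which population the tolerability result describes. If the denominator is left open, it can be chosen after the results are seen.

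**Working it through.** **Inputs.** Table 3 under the rationale for Aim 3 (26 patients, N-13 ammonia) gives the summed stress score (SSS) as 9.1 ± 5.7 with exercise and 6.9 ± 5.9 with dipyridamole, correlation 0.80. The adequacy statement describes an N-13 ammonia study but carries the citation number of the rubidium study; I take Table 3 as the intended basis. The plan states no power, sidedness, primary score or test for Aim 3. I assume a paired t-test, two-sided 0.05.

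**Reproducing 24.** Mean difference = 9.1 − 6.9 = 2.2. SD of differences = √(5.7² + 5.9² − 2 × 0.80 × 5.7 × 5.9) = √13.49 = 3.67. Standardised difference = 2.2/3.67 = 0.60. Noncentral-t power at n = 24 is 80%, so 24 matches this effect. The 35 in section VI fits the other scores in the same table at 80% power: summed difference score n = 33, stress defect size n = 34.

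**Pairs actually planned.** In the Synopsis, 5 of the 24 ischemic subjects go to repeat Lexiscan, leaving 24 − 5 = 19. This agrees with the stated 37 Lexercise subjects: 19 ischemic + (16 − 8) normal + 10 healthy = 37. Power at 19 is about 70% for SSS (56% for summed difference score, 53% for defect size), before any withholding.

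**Numbers lost.** The documents give no withholding rate; 10-30% is an assumption.

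| Withheld | Ischemic pairs | SSS power, effect unchanged |
|---|---|---|
| 0% | 19 | 70% |
| 10% | 17 | 64% |
| 20% | 15 | 58% |
| 30% | 13 | 51% |

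**Effect diluted.** Suppose a share w is withheld, those highest on a trigger that has correlation ρ with the exercise SSS and is otherwise unrelated to the dipyridamole score. Under bivariate normality the mean difference among completers is 2.2 − (5.7 − 0.80 × 5.9) × ρ × φ(z)/(1 − w) = 2.2 − 0.98 × ρ × φ(z)/(1 − w), where z is the normal quantile at 1 − w and φ the normal density. Power here reflects both lost pairs and dilution.

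| Withheld | ρ = 0.5: difference (power) | ρ = 1.0: difference (power) |
|---|---|---|
| 10% | 2.10 (61%) | 2.01 (57%) |
| 20% | 2.03 (52%) | 1.86 (46%) |
| 30% | 1.96 (43%) | 1.71 (35%) |

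Simulation gives the same values to within rounding.

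**Other stated counts.** Study Methods gives 34 with reversible defects. Then 34 − 5 = 29 pairs gives 88% power, and 10-30% withheld leaves 26-20 pairs and about 83-72%. That section's own allocation does not add up to its 50 subjects (13 + 34 = 47), so it cannot simply replace the Synopsis.

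**Aim 1.** If only ischemic subjects are withheld at 10-30%, 19 − 17 = 2 to 19 − 13 = 6 of the 37 who start the treadmill, or 5% to 16%, have no defined place in the side-effect comparison.

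**The case against.** **Exclusion from Aim 1 is not written down.** A reader might infer that withheld subjects are dropped from the side-effect comparison. The documents do not say so; they are silent. They do provide for recording the reason for test termination, symptoms, ECG and blood-pressure changes, and the reason for premature discontinuation. This stands: for Aim 1 the defect is an undefined denominator. For Aim 3 the missing Lexercise scan follows from the protocol's own definition.

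**Serious events are not deleted.** A reader might take the removal sentence in section IX, or the criterion "Subject experiences a serious or intolerable adverse event", as a data exclusion. It stops further procedures and keeps follow-up. A serious event at the Lexercise visit is itself an Aim 1 observation. Most patients have had their clinical Lexiscan scan before the research visit, so an event at a Lexiscan scan that then prevents Lexercise matters mainly for the 10 healthy volunteers, whose Lexiscan scan is a study visit.

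**The Aim 1 question can be read two ways.** Hypothesis 1 concerns Lexiscan injected during maximal exercise, and subjects never injected cannot inform that. This stands, and it is a reason to report both populations with labels.

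**Triggers are mixed and the rate is unknown.** Hypertension, dizziness or heart block need not track defect size, and the site describes its SPECT experience with the combination as generally well tolerated, though not formally analysed. This stands: complete selection (ρ = 1.0) is an extreme case. It does not remove the loss of pairs.

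**It is a pilot.** True, but the plan still tests at 0.05 for Aims 1 and 2 and asserts an adequate size for Aim 3.

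**Conclusion.** The concern holds for the withholding rule. Following the plan as written loses Aim 3 pairs on ischemia and severe symptoms, and nothing in the analysis covers those subjects. The likely bias in Aim 3 is toward no difference, against Hypothesis 3, so a reader should not infer that the rule manufactures a favourable imaging result. For Aim 1, the result read as written applies only to those who passed the treadmill stage.

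On the Synopsis counts, the size claimed as adequate is not delivered: 19 ischemic pairs and about 70% power, against 24 and 80%. That step comes from allocation and should not be attributed to withholding. Withholding at an assumed 10-30% lowers power further to 64-51% from numbers alone, and shrinks the difference from 2.2 to 2.1-1.96 (ρ = 0.5) or 2.0-1.7 (ρ = 1.0). These figures rest on the SSS effect from an exercise-versus-dipyridamole study, a two-sided paired test, the assumed rate and the assumed selection. They would be milder on the count of 34.

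**What to change.** **Aim 1.** Define the denominator as every subject who starts the Lexercise treadmill test. Report Lexiscan withheld, with its reason, as a tolerability outcome, and show side effects among those actually injected alongside it. State that subjects with serious events stay in the safety analysis.

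**Aim 3.** Compare Lexiscan-scan scores between withheld and completed subjects, and limit the conclusion to patients who can complete Lexercise. State whether withheld subjects are imaged and, if so, how those scans are classified.

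**Sample size.** Reconcile 24, 34 and 35, then restate the expected ischemic Lexercise pairs and the adequacy statement with an explicit withholding assumption. Keeping 24 evaluable pairs would need 24/(1 − w) assigned to Lexercise: 27, 30 or 35 at 10%, 20% or 30% withheld. If the size stays as planned, state the lower power.

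**Reconciliation.** The rule's lead sentence covers any clinical or ECG evidence of ischemia, while its list sets severity thresholds. These must be reconciled, because the extent of selection depends on which applies. No change to the safety rule is proposed.

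The analysis changes are wording and use data already recorded. The cost is that reported tolerability and power will look slightly less favourable.
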